Specific Aim 1. Determine the biomechanics and metabolic costs of level-ground walking for 30 Veterans with unilateral TTAs using their own passive-elastic prosthesis both with and without visual feedback training. Each subject will walk at 1.25 m/s on a dual-belt force-measuring treadmill while they use their own passive-elastic prosthetic foot: 1) with no visual feedback, and then with real-time visual feedback targets of: 2) peak propulsive force from the "no feedback" condition, 3) +20% greater peak propulsive force, and 4) +40% greater peak propulsive force. During these visual feedback trials (2-4), we will ask subjects to match the peak propulsive force displayed on a computer monitor (Fig. 1) with their affected leg (AL). We will also ask subjects to: 5) match symmetric visual feedback of the peak propulsive force from both legs. **Hypothesis 1a:** Because passive-elastic prosthetic feet cannot generate power *de novo*, Veterans with TTAs using such prostheses will adopt compensatory biomechanics in their AL and/or unaffected leg (UL) to match the +20% and +40% greater peak propulsive force conditions with their AL and symmetric peak propulsive forces in both legs when using visual feedback during walking, which will increase asymmetry in other values between legs and worsen dynamic stability. Examples of compensatory biomechanics include greater positive joint work and peak joint power in the AL hip joint and/or UL ankle, knee, and hip joints. **Hypothesis 1b:** Due to the negative relation between peak propulsive force and metabolic cost, the metabolic cost of walking when using a passive-elastic prosthesis will be lowest when subjects use visual feedback of +40% peak propulsive force compared to all other conditions. **Hypothesis 1c:** After a 5-min rest period, subjects using their own passive-elastic prosthetic foot will not retain the biomechanics resulting from the prior visual feedback conditions due to compromised stability.

Specific Aim 2. Determine the biomechanics and metabolic costs of level-ground walking for 30 Veterans with unilateral TTAs using a battery-powered ankle-foot prosthesis both with and without visual feedback training. Each subject will walk at 1.25 m/s on a dual-belt force-measuring treadmill while they use a battery-powered ankle-foot prosthesis (emPOWER, BiONX, Ottobock):

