1) with no visual feedback, and then with real-time visual feedback targets of: 2) peak propulsive force from the “no feedback” condition, 3) +20% greater peak propulsive force, and 4) +40% greater peak propulsive force. During these visual feedback trials (2-4), we will ask subjects to match the peak propulsive force displayed on a computer monitor (Fig. 1) with their AL. We will also ask subjects to: 5) match symmetric visual feedback of the peak propulsive force from both legs. **Hypothesis 2a:** Because the emPOWER generates stance-phase prosthetic ankle joint power and net positive work, Veterans with TTAs using the battery-powered prosthesis will be able to match the +20% and +40% greater peak propulsive force conditions with their AL and symmetric peak propulsive forces in both legs without requiring compensatory biomechanics when using visual feedback during walking, which will improve symmetry between legs and dynamic stability. **Hypothesis 2b:** Due to the negative relation between peak propulsive force and metabolic cost, the metabolic cost of walking when using a powered ankle-foot prosthesis will be lowest when subjects use visual feedback of +40% peak propulsive force compared to all other conditions. **H2c:** After a 5-min rest period, subjects will retain the biomechanics resulting from the visual feedback conditions due to improvements in symmetry, metabolic costs, and stability. **Hypothesis 2d:** Veterans with TTAs will have more symmetric biomechanics, lower metabolic costs, and improved dynamic stability when using powered compared to passive-elastic prostheses across all conditions.

II. Background and Significance:

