Our previous research examined how use of the BiOM battery-powered ankle-foot prosthesis affects the metabolic cost and biomechanics of people with TTAs (n=13) compared to using their own passive-elastic prosthetic foot to walk on level-ground and a range of uphill and downhill slopes (1.25 m/s at 0°, ±3°, ±6°, and ±9°) and to non-amputees (n=20) [10]. For the studies assessing the use of the BiOM, we “tuned” the battery-powered prosthesis for each slope using motion capture and GRF data. We adjusted the tuning parameters until each subject’s prosthetic ankle data matched biological ankle data within two SD. Then, we calculated net metabolic power, individual leg mechanical step-to-step transition work, and individual leg net mechanical work symmetry while subjects used their own passive-elastic prosthesis and the BiOM with the established tuning parameters for each slope. Net metabolic power was 5% lower (better) during walking on uphill slopes of +3° and +6° when subjects used the BiOM compared to their own passive-elastic prosthetic foot ($p<0.05$). Use of the BiOM battery-powered ankle-foot prosthesis did not affect individual leg mechanical step-to-step transition work ($p>0.05$) compared to a passive-elastic prosthetic foot but did improve individual leg net mechanical work symmetry on uphill slopes of +6° and +9° ($p<0.01$). Thus, use of a battery-powered ankle-foot prosthesis reduced metabolic costs and improved biomechanical symmetry during walking on uphill slopes for people with TTAs. It is likely that by using visual feedback of peak propulsive force from the emPOWER, people with TTAs will further improve their biomechanics and metabolic costs during walking.

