We also investigated how use of a passive-elastic prosthetic foot and the BiOM battery-powered ankle-foot prosthesis affect leg joint biomechanics during level-ground and sloped walking. We calculated affected leg (AL) and unaffected leg (UL) prosthetic, ankle, knee, hip, and individual leg positive, negative, and net mechanical work. Use of the BiOM compared to a passive-elastic prosthesis resulted in greater AL prosthetic and individual leg net mechanical work on uphill and downhill slopes. Over a stride, AL prosthetic positive work was 23-30% greater ($p<0.05$) on uphill slopes of +6°, and +9°, prosthetic net mechanical work was 1 to 10 times greater (more positive) ($p\leq0.005$) on all uphill and downhill slopes, and individual leg net mechanical work was 146% and 82% more positive ($p<0.05$) on uphill slopes of +6° and +9°, respectively, with the use of the BiOM compared to a passive-elastic prosthetic foot. Greater prosthetic positive and net mechanical work through the use of a battery-powered ankle-foot prosthesis during level ground [11], uphill, and downhill walking would presumably improve functional mobility in people with TTAs. Within our protocol, we iteratively tuned the BiOM to match average biological ankle sagittal plane range of motion, peak moment, peak power, and net mechanical work from twenty non-amputees at each slope [10]. Then, subjects completed three days of metabolic testing, and a final test session where we measured kinematics and kinetics while subjects used the BiOM. Though subjects used the exact tuning parameters, prosthetic components, and alignment established in the tuning/acclimation sessions for all experimental sessions, they modified the way they walked

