Unified deformable (UD) segment analysis. We will use a UD segment analysis to determine the mechanical power derived from the prosthesis plus the residual shank due to elastic energy storage and return [16]. We will develop a model of each prosthesis as a UD segment to characterize the limb-to-ground interaction during walking. The UD segment power analysis is a mathematical algorithm that synthesizes force and displacement in a shank-based reference frame to quantify the rate of prosthetic energy stored and returned. This analysis does not require an 'ankle' joint to be defined, and thus is well-suited to quantify passive-elastic prosthetic foot mechanics. The UD analysis will allow precise measurement of how changes to the use of passive-elastic or battery-powered ankle-foot prostheses affect overall prosthetic function; in particular, the magnitude of prosthetic energy storage and return during walking. These analyses will help identify causal relationships between prosthetic mechanics and overall walking performance for Veterans with TTAs [16].

Symmetry Index (SI). We will calculate the absolute value of the symmetry index [17-19], which is expressed as a percentage, to establish the magnitude of asymmetry between the AL and UL for

each biomechanical variable (var):
$$SI = \left| \frac{var_{UL} - var_{AL}}{0.5(var_{UL} + var_{AL})} \right| \times 100$$
. These variables will include 3D joint range of motion, peak moment, peak power, net mechanical work, stiffness, and UD power, as

well as peak and stance-average GRFs, individual leg mechanical work, and kinematic timing for each leg.

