We developed our research protocol to ensure an adequate sample size for statistical analyses. We used previous data to calculate statistical power for biomechanical and metabolic variables using G*Power statistical software [25]. We set $\alpha = 0.05$, had a sample

size of 30, and used a paired t-test design. We used data from D'Andrea et al. [14] who compared peak vertical GRFs, peak horizontal GRFs, and sagittal plane H range during walking at 0.75-1.75 m/s for eight participants with unilateral TTAs using a passive-elastic prosthesis compared to a powered ankle-foot prosthesis. We calculated symmetry indices (SI) for these biomechanical variables and found strong statistical power (>0.689) for detecting differences in the first peak vertical GRF and strong statistical power (>0.717) for detecting differences in the peak horizontal braking and propulsive GRF in subjects using their own passive-elastic prosthesis compared to the BIOM battery-powered ankle-foot prosthesis (Table 1). The second peak vertical GRF and sagittal plane H had strong statistical power (1.0) at 1.75 m/s, but moderate to low power at the other walking speeds. Further we used data from Herr & Grabowski [11] to determine the statistical

Table 1. Statistical Power for variables reported by previous studies from 0.75-1.75 m/s.

Variable	Statistical Power
SI 1 st peak vertical GRF	0.689-1.0 [14]
SI 2 nd peak vertical GRF	0.249-1.0 [14]
SI Peak horizontal braking GRF	0.996-1.0 [14]
SI Peak horizontal propulsive GRF	0.717-1.0 [14]
SI Sagittal Plane H range	0.115-0.95 [14]
UL Leading/AL Trailing Leg Mechanical Work	1.0 [11]
Metabolic Cost (0.75-1.75 m/s)	0.655-1.0 [11]

power for UL leading leg and AL trailing leg mechanical work and metabolic cost between subjects using their own passive-elastic prosthesis compared to the BiOM battery-powered ankle-foot prosthesis across five walking speeds (0.75-1.75 m/s). We found strong statistical power (1.0) to detect differences in mechanical work and metabolic cost at 1.0-1.75 m/s (Table 1).

G. Summarize Knowledge to be Gained:

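### The symmetry index divides by the signed sum of the legs but is applied to net mechanical work, where opposite signs make it unreadable and, near cancellation, insensitive

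*Combined protocol and SAP*

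**What the plan says.** Section IV.A (Symmetry Index) sets SI = |(UL − AL)/(0.5(UL + AL))| × 100, where UL is the unaffected and AL the affected leg. Its stated purpose is to measure how large the asymmetry is for each biomechanical variable. The list reads "These variables will include 3D joint range of motion, peak moment, peak power, net mechanical work, stiffness, and UD power", and continues, as "well as peak and stance-average GRFs, individual leg mechanical work, and kinematic timing for each leg". The absolute value is taken of the whole ratio, so nothing protects against a sum near zero. There is no rule for opposite signs or for values above 200%.

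Other sections bear on the sign of these variables:

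- Section III treats net work as signed. On slopes, "prosthetic net mechanical work was 1 to 10 times greater (more positive") with the powered device.
- Hypothesis 1a begins "Because passive-elastic prosthetic feet cannot generate power" de novo.
- Hypothesis 2a begins "Because the emPOWER generates stance-phase prosthetic ankle joint power and net positive work".
- Hypothesis 2d predicts that "Veterans with TTAs will have more symmetric biomechanics, lower metabolic costs, and improved dynamic stability when using powered compared to passive-elastic prostheses".
- Individual-leg work is used in two senses. Section III reports that the earlier powered device "did improve individual leg net mechanical work symmetry on uphill slopes", which is net work. Table 1 in section IV.F has a row for "UL Leading/AL Trailing Leg Mechanical Work", which is work by leading and trailing role.

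**The concern.** An index of this form works for quantities that are positive in both legs, such as range of motion or a force peak. For a signed quantity the denominator can shrink towards zero while the numerator stays large.

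The ankle is the likely place. A passive foot cannot add energy, so its net work should not be positive (an inference from Hypothesis 1a). The powered device is said to give positive net work. If UL ankle net work is positive, which is an assumption, the legs have opposite signs in the passive condition, and the device comparison in Hypothesis 2d can cross a sign change.

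Individual-leg work is exposed too if it means net work. In level walking at constant speed the two legs' net work should roughly cancel. That is a mechanical argument; the documents give no values. If leading and trailing work is meant, this second case does not arise.

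Hypotheses 1a, 2a and 2d all predict changes in symmetry between legs. At stake is the ability to detect and interpret such changes in net work.

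**Working it through.** **The plan's own figures.** Table 1 gives SI power for ground-reaction-force peaks and sagittal H range only. Its mechanical-work row (1.0) is not labelled as an SI. No means or SDs are given, so there is no net-work SI figure to reproduce.

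**Algebra from the stated formula.** For opposite signs, SI = 200(|UL| + |AL|)/| |UL| − |AL| |. The numerator sum is larger than the denominator difference, so SI > 200% always. With UL = 0.20:

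| AL | gap UL − AL | half-sum, absolute value | SI |
|---|---|---|---|
| +0.05 | 0.15 | 0.125 | 120% |
| −0.05 | 0.25 | 0.075 | 333% |
| −0.10 | 0.30 | 0.05 | 600% |
| −0.15 | 0.35 | 0.025 | 1400% |
| −0.20 | 0.40 | 0 | undefined |
| −0.40 | 0.60 | 0.10 | 600% |

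With UL fixed, SI rises with the gap up to cancellation and falls beyond it.

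**Power, by simulation.** The inputs from section IV.F are n = 30, alpha 0.05 and a paired t-test. That section names the t-test only for the power calculation, so a signed-rank test is shown as well. Everything else is assumed: two-sided testing, normal and independent legs, within-subject SD 0.015 J/kg per leg and condition, between-subject SD 0.02 to 0.04 J/kg, and the mean work values. There were 10,000 trials per setting, fewer for the signed-rank test.

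For an effect of 0.03 J/kg, the SD of the paired change in the gap is √(4 × 0.015²) = 0.03. The standardised effect on UL − AL is therefore 0.03/0.03 = 1.0.

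(1) Ankle, feedback contrast: UL 0.20, AL rises by 0.03. Ranges run over the two between-subject SDs.

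| AL starts at | t-test on SI | signed-rank on SI | t-test on \|UL − AL\| |
|---|---|---|---|
| −0.20 | 2–6% | 14–29% | 99.9–100% |
| −0.15 | 13–44% | 82–100% | 99.9–100% |
| −0.10 | 37–89% | about 100% | 99.9–100% |
| −0.05 | 76–100% | 100% | 99.9–100% |

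(2) Ankle, device contrast: UL 0.20, AL from between −0.20 and −0.05 to +0.05, between-subject SD 0.04. The t-test on SI has 74–90% power; signed-rank on SI and the t-test on |UL − AL| both have 100%. Median SI falls from 333–1953% to 120%.

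(3) Individual-leg net work, if that is meant: gap from 0.15 to 0.12, sum of the legs unchanged.

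| mean leg sum | t-test on SI | signed-rank on SI |
|---|---|---|
| 0–0.05 | 3–4% | 13–30% |
| 0.10 | 9–42% | 58–73% |
| 0.15 | 41–90% | 85–94% |
| 0.20 | 81–98% | 95–99% |
| 0.30 or more | 99–100% | 99–100% |

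Here |UL − AL| has at least 99.9% throughout.

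Significant t-test results in the wrong direction were at most 0.3% across (1) to (3). They become common only if AL absorbs more than UL generates. For example, AL from −0.30 to −0.27 narrows the gap from 0.50 to 0.47, but SI rises from 0.50/0.05 = 1000% to 0.47/0.035 = 1343%. Nothing in the documents places the data there, and the conclusion does not rest on it.

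**The case against.** The algebra is not in dispute; occurrence, reach and size are.

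- **Occurrence is inferred.** No section reports level-ground net work by leg or joint, and the net-work results in section III are for slopes. This stands: how near the data lie to cancellation cannot be known from the documents.
- **The equal-600% example uses AL = −0.40,** beyond cancellation, where nothing suggests ankle work will lie. True; it illustrates the formula and does not forecast the data. Non-monotonicity matters in practice only if subjects straddle cancellation, or if leg sums lie near zero.
- **Opposite signs alone do not cost power.** The 0.03 effect puts |UL − AL| at its ceiling. With an effect of 0.015 (standardised effect 0.5) and between-subject SD 0.02, AL starting at −0.05 gives 90% for the t-test on SI, 93% for signed-rank on SI and 75% for |UL − AL|. At −0.10 the figures are 59%, 85% and 75%. With SD 0.04, the t-test on SI at −0.05 drops to 46%. So SI can win away from cancellation, and the loss belongs to the approach to it. The percentages remain hard to read either way.
- **The device comparison survives.** Power of 74–90% with direction kept is in line with lower ends that Table 1 already accepts (0.655 to 0.717). This also stands.
- **The reach is narrow.** Net work is one of about ten listed variable families, and Hypothesis 1a's examples of compensation concern positive work and peak power. This limits the severity, but the plan still names net work for this index.

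**Conclusion.** The concern holds. As written, the plan applies an index that cannot measure the size of asymmetry once the legs differ in sign. Values above 200%, the undefined point and the non-monotone behaviour follow from the stated formula alone.

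The power loss is conditional on the assumed work values and SDs. Near cancellation it is severe: 2–6% for the ankle feedback contrast with AL starting at −0.20, and 3–4% for individual-leg net work with sums of 0 to 0.05, both for the t-test on SI. A rank test recovers much of it at the ankle but not at cancellation. The smaller feedback contrasts within a device suffer most.

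The SI of same-sign variables, the force-peak and H-range outcomes in Table 1, the 5% rule for propulsive-force symmetry in section IV.E, metabolic cost and the sample size are unaffected. This should be corrected before analysis, but it does not threaten the trial as a whole. Confidence is medium because the signs of level-ground net work are not documented.

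**What to change.** In section IV.A:

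1. Analyse net joint work, individual-leg net work and any unified-deformable quantity that can be negative as UL − AL in J/kg or W/kg. Use |UL − AL| where the size of the asymmetry is the question.
2. Restrict SI to variables that have the same sign in both legs.
3. State whether individual-leg work is positive, negative or net, and over which phase of the stride.

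Changing the denominator to 0.5(|UL| + |AL|) is not an adequate substitute: it gives exactly 200% for every opposite-sign pair.

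The cost is wording only, with the same data and no extra testing. The drawback is that these asymmetries will be in physical units and not directly comparable with the percentages for other variables. Settling this in advance also avoids deciding what to do with extreme SI values after they have been seen.

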Metabolic Cost. Each metabolic trial will be five minutes long and at least five minutes of rest will be enforced between trials. We will measure rates of oxygen consumption and carbon dioxide production using indirect calorimetry (ParvoMedics TrueOne 2400, Sandy, UT) and will calculate average steady-state metabolic power (W) from minutes 3-5 of each trial using a standard equation [15]. We will subtract the metabolic power required for standing from the metabolic power required for walking to determine net metabolic power (W/kg). A trial length of five minutes is typically more than adequate for participants to reach steady state metabolic rates. To ensure that we measure metabolic rates during steady-state activity, we will verify all data, and if needed, the trial length will be adjusted. We will minimize day-to-day variability by asking subjects to fast and drink nothing but water at least two hours prior to their experimental session, scheduling sessions at the same time of day, and scheduling sessions that are separated by at least 22 hours and no more than two weeks.

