inclusion/exclusion criteria will minimize any potential confounding variables, thereby increasing the internal validity of the proposed studies. Any person matching the inclusion criteria of the study, regardless of race or gender, will be recruited to participate.

Women and/or minorities will be included in the proposed study. Anyone matching the inclusion criteria of the study, regardless of race, sex, or ethnicity will be recruited to participate.

B. Study Design and Research Methods

Before participants are enrolled in each study, we will complete a pre-screening form and each participant will be asked to give informed written consent. We will ensure that all participants understand the consent form and protocol prior to participation.

Subjects will be asked to complete an acclimation session and three experimental sessions at the VA ECHCS/University of Colorado Applied Biomechanics Lab. The experimental sessions will be on a separate day at the same time of day, and each session will require approximately 2 hours of time. On each day, we will measure subject's height, weight, and limb segment lengths. Then, we will place reflective markers on their legs and torso using double-sided tape. These markers will allow us to track their body position using our motion capture system. We will also record the forces that they exert on the ground using a force-measuring treadmill. Further, on days 2-4 we will measure their leg muscle activity using wireless electrodes that will be placed over their muscles using double-sided tape and their metabolic rates from the air that they breathe out into a mouthpiece. On days 2-4, we will ask subjects to perform a 30-60 sec walking trial at 1.25 m/s using their own prosthesis.

Day 1 – Acclimation Session. We will determine the strength of subject's lower limb muscles using an isokinetic dynamometer (Biomedex Medical Systems, Shirley, NY). Then, our prosthetist will align the emPOWER (BiONX, Ottobock, Duderstadt, Germany) battery-powered ankle-foot prosthesis to each subject. We will attach reflective motion capture markers to their legs and pelvis using double-sided tape and Velcro straps, and tune the emPOWER prosthesis by having them walk on a force-measuring treadmill at 1.25 m/s for a series of ~45 sec trials. Then, we will give them additional time to walk using the emPOWER prosthesis.

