Days 2, 3 and 4 – Experimental Sessions. We will ask subjects to fast and drink nothing but water for at least 2 hours prior to each experimental session. On each day, we will attach reflective motion capture markers to their legs and pelvis using double-sided tape and Velcro straps, and surface electrodes over their leg muscles using double-sided tape and elastic wraps. We will mark the locations of each electrode with "permanent" marker on their skin. Then, we will ask subjects to walk for 30-60 sec at 1.25 m/s (2.8 mph) using their own prosthesis.

On Days 2, 3, or 4, we will ask subjects to walk at 1.25 m/s on a dual-belt force-measuring treadmill while we measure their metabolic rates, biomechanics, and muscle activity using their own passive-elastic prosthetic foot for:

- 1) 5 min with no visual feedback
- 2) 5 min with real-time visual feedback of affected leg (AL) peak propulsive force from the "no feedback" condition, and 5 min with no visual feedback
- 3) 5 min with real-time visual feedback of +20% greater AL peak propulsive force than the "no feedback" condition, and 5 min with no visual feedback
- 4) 5 min with real-time visual feedback of +40% greater AL peak propulsive force than the "no feedback" condition, and 5 min with no visual feedback
- 5) 5 min with real-time visual feedback of AL peak propulsive force and unaffected leg (UL) peak propulsive force, and 5 min with no visual feedback

On Days 2, 3, or 4, we will ask subjects to walk at 1.25 m/s on a dual-belt force-measuring treadmill while we measure their metabolic rates, biomechanics, and muscle activity using the emPOWER battery-powered ankle-foot prosthesis for:

- 1) 5 min with no visual feedback

- 2) 5 min with real-time visual feedback of AL peak propulsive force from the “no feedback” condition, and 5 min with no visual feedback
- 3) 5 min with real-time visual feedback of +20% greater AL peak propulsive force than the “no feedback” condition, and 5 min with no visual feedback
- 4) 5 min with real-time visual feedback of +40% greater AL peak propulsive force than the “no feedback” condition, and 5 min with no visual feedback
- 5) 5 min with real-time visual feedback of AL peak propulsive force and UL peak propulsive force, and 5 min with no visual feedback

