We will enforce 5 minutes of rest between trials. During the real-time visual feedback trials, we will ask subjects to match the power magnitude displayed on a computer screen placed in front of them with their AL and/or UL for those 5 minutes. Subjects will be asked to perform a maximum of 35 minutes of walking per day and each experimental session will require ~2 hours of time. The total time commitment for this study is approximately 8 hours; 2 hours per day over 4 days.

D. Description, Risks and Justification of Procedures and Data Collection Tools:

We propose to study healthy people who are familiar with using a prosthesis because this choice minimizes any potential confounding factors associated with novel prosthetic use. Walking requires low exercise intensity, yet poses no more than minimal cardiac risk for this population. We will restrict our patient age range to comply with the American College of Sports Medicine guidelines. The American College of Sports Medicine (ACSM) Guidelines for Exercise Testing and Prescription (Ninth edition, 2014) classify individuals of any age as having low or moderate risk to participate in an exercise program if they present no more than two of the following risk factors: males age \geq 45 yrs, females age \geq 55 yrs, first degree family history of coronary artery disease, cigarette smoking, sedentary lifestyle, obesity, hypertension, dyslipidemia (high cholesterol), and pre-diabetes. These guidelines further recommend that a medical exam and diagnostic exercise testing are not warranted prior to beginning a moderate exercise program for individuals at low to moderate risk. We are being conservative by including patients under 67 years of age (i.e. before their 67th birthday) who do not have any of the other risk factors listed above.

We will comply with Good Clinical Practices (GCPs) by upholding standards for the design, conduct, performance, monitoring, auditing, recording, analysis and reporting of our clinical studies, and by protecting the rights, safety, and well-being of human subjects. We will assure the quality, reliability, and integrity of data collected. We will maintain and monitor GCPs by obtaining Institutional Review Board (IRB)-approval, requiring informed consent, having a data-monitoring plan, reporting Adverse or Serious Adverse Events, having proper documentation, and validating our data collection and reporting procedures.

Foreseeable risks:

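### Each prosthesis needs 45 min of walking against a 35-min daily cap, so at least one feedback condition per prosthesis is compared with a no-feedback reference from another day

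*Combined protocol and SAP*

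**What the plan says.** Section IV.B plans one acclimation day and three experimental days: "Subjects will be asked to complete an acclimation session and three experimental sessions". The trial list for each prosthesis opens with the same sentence, "On Days 2, 3, or 4, we will ask subjects to walk at 1.25 m/s on a dual-belt force-measuring treadmill while we measure", so neither prosthesis is tied to a day.

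Each list starts with "1) 5 min with no visual feedback". Items 2 to 5 are the four feedback conditions: the baseline force level (+0%), +20%, +40%, and symmetric feedback of both legs. Each is 5 min of feedback followed by 5 min without. The +40% item, for example, begins "4) 5 min with real-time visual feedback of +40% greater AL peak propulsive force than the" baseline condition and ends with its own no-feedback trial. The initial no-feedback trial appears once per list, and the first three feedback targets are set from it.

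The cap follows the lists: "Subjects will be asked to perform a maximum of 35 minutes of walking per day". The same section adds a short daily walk: "On days 2-4, we will ask subjects to perform a 30-60 sec walking trial at 1.25 m/s using their own prosthesis". Section IV.A (Metabolic Cost) recognises variation between days and limits it by fasting, a fixed time of day and "scheduling sessions that are separated by at least 22 hours and no more than two weeks". Section F (Data Analysis Plan) gives a power calculation for a paired t-test. It contains no day allocation, no rule for a same-day reference and no day term.

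**The concern.** The trial list for one prosthesis is longer than a day's permitted walking, yet the reference for that prosthesis is scheduled only once. Some feedback conditions must therefore be set against a no-feedback trial from a different session, possibly up to two weeks away. Between sessions the markers and electrodes are re-applied, the standing metabolic baseline may differ, and the subject may walk differently.

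Hypotheses 1b and 2b compare the +40% condition with all other conditions, and hypotheses 1a, 1c, 2a and 2c rest on contrasts with no feedback. Any contrast that crosses days contains the feedback effect plus whatever changed between sessions. Where a target-based condition moves to another day, its +20% or +40% is also relative to a force measured in another session. The analysis plan has nothing to separate these components.

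**Working it through.** **Inputs, all from section IV.B.** Three experimental sessions; 5-min trials; per prosthesis one baseline and four feedback/follow-up pairs; a cap of 35 min per day; a 30-60 sec own-prosthesis walk each day. The 35 min is a stated limit, so there is nothing to reproduce. The stated total commitment does reproduce: 4 days x 2 h = 8 h.

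**Assumptions.** (a) A feedback trial and its follow-up stay on one day, because hypotheses 1c and 2c define retention after a 5-min rest. (b) The baseline comes before the feedback trials of the same prosthesis, as section I states.

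**Walking per prosthesis.** 1 + 4 x 2 = 9 trials; 9 x 5 = 45 min, which exceeds 35. Both prostheses: 18 trials, 90 min; 90 / 3 = 30 min per day, or 30.5 to 31 min with the short walk. The total fits. Session length is not the obstacle: nine trials with eight 5-min rests take 45 + 40 = 85 min of about 120.

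**Short walk outside the cap.** 35 / 5 = 7 trials per day.
- Fewest off-day: a baseline plus three pairs is 1 + 3 x 2 = 7, so a fourth pair never fits. At least 1 of 4 conditions per prosthesis is off its reference day, 2 of 8 overall. Days of 35, 35 and 20 min achieve this: baseline, +0%, +20% and +40% of one prosthesis on the first day, the same for the other prosthesis on the second, and both symmetric pairs on the third (4 x 5 = 20 min).
- Most off-day: a day holds at most three pairs (four need 8 trials), so the last two days hold at most six. At least 8 - 6 = 2 pairs fall on the first day, and by (b) these share their baseline's day. At most 6 of 8 are off-day.

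**Short walk counted.** 7 x 5 + 0.5 to 1 = 35.5 to 36 min, which exceeds 35, so six trials fit per day. Three days give 18 slots for 18 trials, so every day is full. Pairs fill slots in twos, so a six-slot day cannot hold exactly one baseline, and both baselines share a day. By (b) that is the first day. It then has 6 - 2 = 4 slots, or two pairs, and exactly 8 - 2 = 6 of 8 feedback conditions fall on a later day (at least 2 per prosthesis). An exhaustive listing of the allocations confirms both ranges.

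**Same-day references available on a later day.** The short walk uses the subject's own prosthesis only, so it does not cover the emPOWER. At 30-60 sec it also cannot supply metabolic power, which section IV.A averages over minutes 3-5. The other 5-min no-feedback trials follow feedback and test retention. Hypothesis 2c predicts that feedback effects persist in them, so they are not clean references.

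**The case against.** The strongest reply is that the lists run over three days by design and that 90 min divides comfortably into three sessions. Where seven trials fit, only the symmetric condition need move, and it uses no target derived from the baseline. The +40% contrasts with no feedback, +0% and +20% can then all be same-day. The 6 of 8 figure needs the short walk to count toward the cap, which the protocol does not say; a cap of 35 = 7 x 5 may well be meant to count only 5-min trials. Day-to-day variation is partly controlled by fasting, time of day, session spacing, subtraction of standing metabolic power and marked electrode sites. Marker re-placement does not affect forces measured by the treadmill. All of this stands.

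It rules out several stronger readings that a reader might infer:
- That the protocol is infeasible or contradicts itself on total walking. It does not; the schedule is unstated.
- That every off-day condition uses another day's target. The symmetric condition does not.
- That the 37% lower net work in section III measures the day effect. That figure is for a different powered device (BiOM) and a different quantity, and covers all slopes but one. It compares tuning with a final session after three days of metabolic testing, so acclimation may explain it. It says nothing direct about peak propulsive force or metabolic power across Days 2-4 here.

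The reply does not remove the core. No schedule under the stated assumptions puts all four feedback conditions on the day of their reference, and the protocol does not commit to the schedule that limits the problem.

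**Conclusion.** The point holds in a limited form and should be addressed. Even in the best layout, one feedback condition per prosthesis, and so at least one of the comparisons in each of hypotheses 1b and 2b, crosses days. The gap is widest for net metabolic power with either prosthesis and for every emPOWER outcome, because no untrained same-day reference is listed for a later day. For own-prosthesis force and kinematics the daily short walk could serve, but the plan gives it no such role.

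The documents give no between-day standard deviation, so the effect on any estimate or on power cannot be computed. If all subjects follow one schedule, the day effect may act as bias; if the allocation varies, it may be mainly added variance. The counts rest on three sessions, intact pairs and baseline-first order.

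**What to change.** 1. Reconcile the trial list with the cap: state which trials go on which day and whether the short walk counts toward the 35 min. Where seven trials fit, keep the baseline and the +0%, +20% and +40% conditions of a prosthesis on one day, so that only the symmetric condition moves.
2. State that each feedback trial and its no-feedback follow-up are done on the same day.
3. On each day the emPOWER is used, add a 30-60 sec no-feedback emPOWER walk before any feedback. Use it and the existing own-prosthesis walk as same-day references for force and kinematics, not for metabolic cost.
4. Vary the day allocation of the off-day conditions across subjects and include session day in the model. Otherwise report the off-day contrasts, above all net metabolic power, as cross-day comparisons. Under a single fixed schedule a day term cannot be separated from condition. In the 35/35/20 layout the first two days are full, so the symmetric pairs always fall on the third day and the reporting alternative applies.
5. Do not use the post-feedback retention trials as the metabolic reference.

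**Cost.** About 1 min more walking on emPOWER days, which must itself fit the cap: a six-trial day becomes 6 x 5 + 1 + 1 = 32 min. A seven-trial day is already at 35 min, so there the extra walk fits only if short walks are declared outside the cap. The day term uses a few degrees of freedom. Repeating the full 5-min baseline on every day a prosthesis is used would give a metabolic reference, but it needs 20 trials (100 min). These fit as 35/35/30 min only if short walks are not counted; with six trials per day there are only 18 slots.
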